Excelencia en oftálmicos

Study Protocol:

SOPH185-0521/I

Title: Phase I clinical study to evaluate the safety and tolerability of PRO-185 ophthalmic solution applied in clinically healthy subjects

Sponsor: Laboratorios Sophia, S.A. de C.V.

Version Date: July 27, 2022

Version: 2.0

This document was prepared in accordance with FDA, ICH, and GCP guidelines.

Change History

Sections, paragraphs and subsections	Main modifications made
Cover Page Headers and Footers	Updated version number, version date, and page count.
Change History	Added Change History to describe the major changes between this version and the previous one.
Content	Section page numbers have been changed, and new subsections have been added.
Index of tables, graphs and figures	The page numbers of tables and figures were modified, and the table of contents of graphs was added.
Study leaders	The Study Director's affiliation was changed from "Medical Manager" to "Regional Clinical Research Manager."
List of abbreviations	The abbreviation TRPL is being dropped. Tear film break-up time.
1.1 Synopsis	
The protocol version number and version date have been changed.
 
Hypothesis H_0 changed to:
 
"PRO-185 ophthalmic solution is safe and tolerable for ophthalmic use, with any of the following adverse events occurring in 20% or less of subjects: increased intraocular pressure (IOP >5 mmHg), heart rate changes (>15 bpm), increased systemic blood pressure [>15 mmHg systolic (SBP) or >10 mmHg diastolic (DBP)], pharmacological mydriasis, or grade 3 and 4 conjunctival hyperemia." The underlined words "any of" were added to highlight that only one of the adverse events described was necessary. It is described that comparisons will be between pre- and post-treatment measurements at visits 1 and 2 and between measurements at the pre-PT baseline visit and measurements at the final visit.
 
In Statistical Methodology, the Kolmogorov-Smirnov test and the Mann-Whitney U test were changed to the Wilcoxon signed-rank test; the Pearson X^2 test was also changed to the binomial X^2, and the McNemar test was withdrawn .

2.2.1 Naphazoline	Typo fixed.
2.2.3 Menthol	
Typographical and writing errors were corrected.
 
Added information on menthol irritability and toxicity testing.
 
Added information on the usefulness of using menthol.

2.3 Background on the research product	It was added that a preclinical safety and toxicity study of the PRO-185 ophthalmic solution has already been carried out.
2.3.1 Preclinical safety and toxicity study of PRO-185 solution	New section describing the comparative preclinical safety and toxicity study of PRO-185 ophthalmic solution versus a marketed product, Nazil® Contamination . The study involved administering the drugs four times daily for 30 days to New Zealand albino rabbits. The results show no relevant safety and toxicity data for any of the investigational products. There are also no clinical changes or manifestations demonstrating the unsafety or toxicity of the PRO-185 formulation. Therefore, it is concluded that the product is safe and nontoxic for ocular use in the selected animal model.

CONFIDENTIAL

2.3.2 Preclinical study of an ophthalmic solution of naphazoline 0.1% and hypromellose 0.5% (higher concentration of the main components of PRO-185)	Information was added about another preclinical study different from the one already described.
2.5.1 Known potential risks	Typos were fixed. Information on the safety of menthol as an excipient is added to the concentration found in the PRO-185 solution.
2.7 Justification of the study	Information related to the preclinical study of PRO-185 is added, as well as the safety of menthol and its use at the concentration found in the PRO-185 solution.
3.2 Hypothesis	or "any of" are added to specify that only one of the adverse events described in the hypothesis must occur at the frequency also described. It is specified that comparisons will be made between pre- and post-treatment measurements from visits 1 and 2, and between measurements from the pre-PT baseline visit and measurements from the final visit.
Table iii . Operational definition of variables in 7.4.4 Definition of variables, methods and scales for their measurement	The Statistical Tests of all variables in the table are modified.
7.4.5.7 SICCA ocular surface staining	The statement is removed: After evaluating the TRPL, between 4 and 8 minutes after instillation of the dye.
10.1.1 Calculation methodology	Typo corrected.
10.1.2 Size calculation	Typographical errors are corrected. The equations for calculating the sample size are modified. Absolute values are added in parentheses to the description of the signs.
10.2 Clinical data management	Typo corrected.

H_1	Alternative hypothesis
ICH	International Council on Harmonization (International Council for Harmonization)
ICMJE	International Committee of Medical Journal Editors (ICME) of Medical Journal Editors)
IP	Principal Investigator
IP ₃	Inositol triphosphate
ITT	By intention to treat (ITT) to Treat)
bpm	Beats per minute
mmHg	Millimeters of mercury
NOM	Mexican Official Standard

WHO	World Health Organization
PAD	Diastolic blood pressure
PI	Research product
PIO	Intraocular pressure
PNA	Unanticipated problems
Pre-TP	Prior to applying TP Ofteno [®]
Post-Tx	Post-treatment
PP	Population by protocol
Post -TP	After application of TP Ofteno [®]
Pre -Tx	Pre-treatment
RAM	Adverse drug reaction
RNEC	National Registry of Clinical Trials
SDV	Source Document Verification Document Verification)
SICCA	Sjögren 's International Collaborative Clinical Alliance)
SPSS	Statistical Package for the Social Sciences (Statistical Package for the Social Sciences) Package for the Social Sciences)
SRAM	Suspected adverse drug reaction
TEROS 40	Tear evaporation rate at 40% ambient humidity (Tear Evaporation Ocular Surface Rate)
TF	Fluorescein staining
TVL	Lissamine green staining
TRPM8	Cation receptor potential channel subfamily 8 (Transient Receptor Potential) Cation Channel Subfamily M Member 8), also known as the cold-sensing cation channel.
UFTLS	Pharmacovigilance and Technovigilance Unit of Sophia Laboratories
VV	Current version
X ²	Chi-square
°C	Degrees Celsius

1. Summary of the protocol

1.1 Synopsis

Title of the study: Phase I clinical study to evaluate the safety and tolerability of PRO-185 ophthalmic solution applied in clinically healthy subjects	
Study number: SOPH185-0521/I	Creation date: 05/17/2021
Protocol version: 2.0	Version date: 27/07/2022
Therapeutic indication: Ocular vasoconstrictor	Use: Conjunctival hyperemia
Estimated duration of the study (from the first visit of the first patient to the preparation of the final report) : 5 months	Clinical development phase: Yo
Goals: Main objective: 
• To evaluate the safety and tolerability of PRO-185 ophthalmic solution in ophthalmologically and clinically healthy subjects. Specific objectives: 
• To evaluate the safety of PRO-185 ophthalmic solution by measuring the incidence of subjects experiencing an increase of >5 mmHg in intraocular pressure 20 minutes after application compared to the initial value.• To evaluate the safety of PRO-185 ophthalmic solution by measuring the incidence of subjects experiencing a heart rate variation of >15 beats per minute 20 minutes after application.• To evaluate the safety of PRO-185 ophthalmic solution by measuring the incidence of subjects with an increase in systolic blood pressure of >15 mmHg or >10 mmHg in diastolic blood pressure 20 minutes after application.	

- To assess tolerability by the incidence of grade 3 and 4 conjunctival hyperemia.
- To assess tolerability by the incidence of pharmacological mydriasis.
- Evaluate tolerability by the incidence of expected and unexpected adverse events.

Hypothesis :

H_0 = PRO-185 ophthalmic solution is safe and tolerable for ophthalmic use, as it occurred in 20% or less of subjects with any of the following adverse events: increased intraocular pressure (IOP >5 mmHg), heart rate variation (>15 bpm), increased systemic blood pressure [>15 mmHg systolic (SBP) or >10 mmHg diastolic (DBP)], pharmacological mydriasis, or grade 3 and 4 conjunctival hyperemia.

$$H_0: p - p_0 \leq \delta$$

H_1 = PRO-185 ophthalmic solution is not safe or tolerable for ophthalmic use because more than 20% of subjects experienced any of the following adverse events: increased IOP (>5 mmHg), heart rate variation (>15 bpm), increased systemic blood pressure [>15 mmHg systolic (SBP) or >10 mmHg diastolic (DBP)], pharmacological mydriasis, or grade 3 and 4 conjunctival hyperemia.

$$H_1: p - p_0 > \delta$$

Comparisons will be made between pre- and post-treatment measurements from visits 1 and 2, and between measurements from the baseline visit (before PT application) and measurements from the final visit. Only one of the adverse event values described in the hypothesis need be abnormal with a frequency >20% between the comparisons (pre-treatment with post-treatment; or pre-PT baseline with values from the final visit) for the null hypothesis to be rejected.

Study design:

Phase I clinical study, controlled, non-comparative, open, single-center

Number of subjects (planned and analyzed):

Number of subjects planned: 22 subjects.

Diagnosis and main inclusion criteria:

- Ophthalmologically and clinically healthy subjects.

Selection criteria:

Inclusion criteria:

- Be clinically healthy.

- Have the ability to voluntarily grant signed informed consent.
- Be able and willing to comply with scheduled visits, treatment plan, and other study procedures.
- Be between 18 and 45 years old.
- Women of childbearing potential must ensure continued use (started \geq 30 days prior to signing the ICF) of a hormonal contraceptive method or intrauterine device (IUD) during the study period.
- Have a best-corrected visual acuity of 20/30 or better in both eyes.
- Have vital signs within normal parameters.
- Have an intraocular pressure \geq 10 and \leq 21 mmHg.

Exclusion criteria:

- Be a user of topical ophthalmic products of any kind.
- Being allergic to naphazoline or having a history of intolerance to nasal decongestants or ocular vasoconstrictors.
- Have a history of a suspected diagnosis of primary angle closure, primary angle closure, or angle-closure glaucoma.
- Having iridotomies or waiting for iridotomies.
- Have conjunctival hyperemia grade 3 and 4 on the Efron scale.
- Have ocular surface staining with a value equal to or greater than 3 on the SICCA scale in either eye.
- Being a user of medications or herbal products, by any other route of administration.
- For women: be pregnant, breastfeeding, or planning to become pregnant during the study period.
- Having participated in clinical research studies 90 days prior to inclusion in this study.
- Having previously participated in this same study.
- Be a contact lens user who cannot discontinue use during the study.
- Having a history of any chronic-degenerative disease, including diabetes and high blood pressure.
- Present inflammatory or infectious disease, active at the time of entering the study.
- Present unresolved injuries or traumas at the time of entering the study.
- Have a history of any type of eye surgery.
- Having undergone non-ophthalmological surgical procedures in the last 3 months.

Research Product (RP):

- PRO-185. Naphazoline 0.03% and hypromellose 0.2%. Solución oftálmica. Laboratorios Sophia, S.A. de C. V., Zapopan, Jalisco, Mexico.
- Dosage : 1 drop 4 times a day in both eyes (AO).
- Route of administration: Ophthalmic.

Duration of treatment:	Subject's duration in the study:
8 days	10 days

Evaluation criteria:**Primary outcome variables**

- Intraocular pressure
- Heart rate
- Systemic blood pressure
- Pupillary diameter
- Conjunctival hyperemia

[figure not shown]
Secondary outcome variables:

- Best corrected visual acuity
- Changes in ocular surface staining
- Incidence of chemosis
- Incidence of expected adverse events
- Incidence of unexpected adverse events

Statistical methodology

Statistical analysis will be performed using specialized statistical software (SPSS statistical package, available version, or R software). Quantitative variables will be expressed as measures of central tendency: mean, median, standard deviation, and ranges. Qualitative variables will be presented as frequencies and percentages. Statistical analysis to rule out differences will be performed using nonparametric statistics, using the Wilcoxon signed-rank test for one sample, for quantitative variables. Analysis between qualitative variables will be performed using the binomial X² (Chi-square) test or Fisher's Exact test (when applicable). An alpha (α) ≤ 0.05 will be considered significant .

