2.3.3 Clinical study of an ophthalmic solution of naphazoline 0.1% and hypromellose 0.5%

An open-label, single-center, observational, prospective clinical study included thirty healthy volunteers. Volunteers were administered a 0.1% naphazoline and 0.5% hypromellose solution four times daily for ten days. Results showed no changes in conjunctival hyperemia, conjunctival discharge, ciliary injection, chemosis, and rose bengal and fluorescein staining. However, 86% of patients experienced burning, 70% of which was mild and the remainder moderate; 6.6% had mild red eyes; and 6.6% had mild ocular pain. The mean burning score was 0.6861, with a standard deviation of 0.42 and a standard error of 0.016. Student's t-test showed a $p > 0.05$, leading to the conclusion that the burning score was not statistically significant. The study concludes that the solution of naphazoline 0.1% and hypromellose 0.5% is safe for application to the ocular surface of healthy volunteers. [28]

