2.7 Justification of the study

Laboratorios Sophia, SA de CV, has conducted a preclinical and phase I clinical study of a similar formulation, but with a higher concentration of components. The reduction in the concentration of the main components (naphazoline and hypromellose) in the PRO-185 solution compared to this formulation studied could mean greater safety of PRO-185, but not necessarily greater tolerance, since the excipients may be involved in clinical manifestations unrelated to the main components.

Menthol has been used in ophthalmic preparations to relieve visual fatigue and ocular discomfort. [23] The inclusion of menthol among the excipients in PRO-185, as well as the lack of clinical evaluation of this formulation, necessitates clinical evaluation of the product. This would provide a more complete safety and tolerability profile.

In a preclinical safety and toxicity study of PRO-185 ophthalmic solution in New Zealand albino rabbits, the drug was shown to be non-toxic and safe to administer. Information also indicates that, at the menthol concentration used in Draize tests, there were no irritating or toxic effects.

Because there is preclinical evidence of safety and toxicity with the PRO-185 formulation, as well as the absence of irritation at the concentration used; and because there are ophthalmic products with menthol as an excipient in similar combinations on other markets, it was decided to advance to clinical research to test the safety and tolerability of PRO-185 in a controlled environment with healthy subjects.

3. Objectives and hypotheses

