6.1.3 Treatment with the investigational product

The investigational product will be administered at the conclusion of the baseline visit, and the subject will administer the drops approximately every 2-4 hours between drops, applying them a total of 4 times per day to each eye.

Baseline visits, 1, and 2, should be completed in the morning, before 11 a.m., to allow the patient more time to apply PRO-185 throughout the day. During visits 1 and 2, the patient will come to the clinic without having previously applied the investigational product. The first application will be considered the drop applied by the researcher during the visit. For visit 1, the patient will be required to apply the product three times after the visit has concluded. For visit 2, the patient will not need to apply the product again because the investigational product will have been returned to the researcher.

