7.4.2 Secondary outcome variables

- Best corrected visual acuity (BCVA).
- Changes in ocular surface staining.
- Incidence of chemosis.
- Incidence of expected adverse events.
- Incidence of unexpected adverse events.

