7.4.5.9 Adverse events

As described in subsection 8.2 Definition of Adverse Event , an adverse event is defined as Any adverse medical occurrence in a subject to whom an investigational product is administered, regardless of causal attribution.

The management of adverse events will be carried out in accordance with the provisions of Section 8. Evaluation and management of adverse events and incidents.

The Principal Investigator will record any adverse events that may occur in the study subjects in the corresponding section of the eCRF and will also report them in the clinical record.

For an adequate assessment of adverse events, in addition to the targeted questioning, a Comprehensive Ophthalmologic Evaluation must be performed at each visit . This evaluation consists of: ophthalmologic examination of the eyelids and adnexa; anterior and posterior segments, which are performed during a routine ophthalmologic examination, procedures not specifically included in the study variables. The posterior pole evaluation may be performed with direct or indirect ophthalmoscopy, with or without pharmacological mydriasis, at the discretion of the PI. The fundus will be assessed for abnormalities that could alter the study results. IOP will be measured during this evaluation, using the PI's chosen instrument, and should be measured after the stain evaluation. The results of the evaluation will be recorded in the clinical record. Only those findings that the Principal Investigator considers to be adverse events will be reported in the eCRF

Adverse events that may occur with PRO-185 are: ocular burning, ocular hyperemia, foreign body sensation, itching, red eye, eye irritation, tearing, little relief of discomfort, blurred vision, burning, superficial punctate keratitis, stinging, mydriasis, increase or decrease in intraocular pressure, release of pigment granules, rebound hyperemia, headache, vertigo, hypertension, hypotension, cardiac irregularities (including tachycardia, bradycardia, among other types of cardiac irregularities), nervousness or excitability, nausea, dizziness, weakness, drowsiness and diaphoresis. [29]

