7.5.10 Delivery of material for the subject

This refers to the provision of the subject's ID card and the subject's diary. The ID card will serve as identification with the treatment assignment number; this card can also serve as an appointment card. The Subject's Diary is used to record the number of times the treatment is administered.

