### 3.4 Subject's duration in the study/treatment

Up to 11 days, 1 drop 4 times a day in both eyes (OE) for 8 days, see Table 1.

[figure not shown]

Figure 1. Study diagram

Table 1. Study schedule

Procedures	Baseline visit		Visit 1		Visit 2		Final visit Day 10 (+1) Without treatment	
	Day 1		Day 3 (+1)		Day 8			
	Pre-Tx	Post-Tx	Pre-Tx	Post-Tx	Pre-Tx	Post-Tx		
FCI Signature	X							
Medical record	X							
Eligibility criteria	X							
Subject code assignment	X							
Adverse events	X	X	X	X	X	X	X	
Heart rate	X	X	X	X	X	X	X	
Frequency respiratory	X		X		X		X	
Blood pressure	X	X	X	X	X	X	X	
Temperature (°C)	X		X		X		X	
Pregnancy test in urine	X						X	
AVMC	X		X		X		X	
Evaluation of the anterior segment		X		X		X		
Pupillary diameter measurement	X	X	X	X	X	X	X	
Eye stains	X	X	X	X	X	X	X	
Intraocular pressure	X	X	X	X	X	X	X	
Evaluation of the posterior segment	X		X		X		X	
Application of the medicine in visit	X		X		X			
Delivery of material for the subject		X						
Delivery of the medication study		X						
Evaluation of medications concomitants	X		X		X		X	
Evaluation of the adherence			X		X			
Return of the medicine of the study						X		
Withdrawal from the diary of subject						X		

Pre-Tx: pretreatment, indicates the assessments to be performed before administration of the investigational drug. Post-Tx: post-treatment, indicates the evaluations to be performed within 20–40 minutes after administration of the investigational drug. ICF: informed consent form. BCVA: best-corrected visual acuity.

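### The diary is described only as a count of drops, so mild symptoms after home doses (26–27 of 29 applications) are at risk of under-reporting

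*Protocol*

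**What the plan says.** **Objective and role.** Protocol 1.1 and 3.1.2 name three tolerability measures: grade 3–4 hyperemia, pharmacological mydriasis, and AE incidence ("Evaluate tolerability by the incidence of expected and unexpected adverse events"). AE incidence is secondary ("Incidence of expected adverse events", Protocol 7.4.2). H0 and H1 in Protocol 3.2 use only IOP, heart rate, blood pressure, mydriasis and hyperemia.

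**Why the trial is run.** Protocol 2.7 argues that lower concentrations need not mean better tolerance, because "the excipients may be involved in clinical manifestations unrelated to the main components". Protocol 7.4.5.9 lists burning, stinging, itching, tearing and blurred vision among the possible AEs.

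**Dosing.** SAP 3.4 gives "1 drop 4 times a day in both eyes (OE) for 8 days". Protocol 6.1.3 adds that the investigator gives one drop at each of visits 1 and 2, that three home drops follow visit 1, and that none follow visit 2. On Day 1, "The investigational product will be administered at the conclusion of the baseline visit", without saying who applies it.

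**Diary.** Protocol 7.5.10: "The Subject's Diary is used to record the number of times the treatment is administered". Protocol 7.5.13 uses it for adherence.

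**AE capture.** Protocol 7.4.5.9 requires that "in addition to the targeted questioning, a Comprehensive Ophthalmologic Evaluation must be performed at each visit". The schedule (Protocol 1.3, Table v) also marks AEs at Post-Tx, 20–40 minutes after the clinic drop. Subjects may notify the investigator between visits (Protocol 8.5.3) or have an unscheduled visit (7.7.5).

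**The concern.** Burning, stinging and itching after a drop are typically brief and leave nothing to see at the slit lamp days later. The sponsor's earlier volunteer study (Protocol 2.3.3) illustrates this: it found no change in hyperemia, chemosis or staining, yet "86% of patients experienced burning". Examination at visits cannot stand in for asking what the subject felt.

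If most drops are taken where nobody asks, and the one document the subject holds is described as counting drops, the recorded symptom rate depends on later recall. Forgotten symptoms can only lower that rate. The product would then look better tolerated than it is, on the question that Protocol 2.7 gives as a reason for the trial.

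**Working it through.** The documents state no application count, home share or capture rate, so there is no plan figure to reproduce. The count below comes from Protocol 6.1.3 and the visit days in Protocol 1.3, with visit 1 on Day 3.

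| Day | Applications per eye | At home | Days to next scheduled AE questioning |
|---|---|---|---|
| 1 | 4 | 3–4 | 2 |
| 2 | 4 | 4 | 1 |
| 3 (visit 1) | 4 | 3 | 5 |
| 4 | 4 | 4 | 4 |
| 5 | 4 | 4 | 3 |
| 6 | 4 | 4 | 2 |
| 7 | 4 | 4 | 1 |
| 8 (visit 2) | 1 | 0 | – |
| Total | 29 | 26–27 | |

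**Home share.** With two clinic drops, 27/29 = 93.1%. If the Day 1 drop is also given in clinic, 26/29 = 89.7%. If only three drops fit on Day 1, the shares are 26/28 = 92.9% and 25/28 = 89.3%. SAP Table 1 marks a clinic application at baseline and the Protocol schedule does not. The two must be reconciled, but this moves the share only between about 90% and 93%.

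**Recall interval.** Of the 26–27 home drops, 8 (Days 2 and 7) are asked about the next day, 7–8 (Days 1 and 6) after two days, and 4 + 4 + 3 = 11 after three to five days. If visit 1 falls on Day 4, the longest interval is 8 − 4 = 4 days.

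**What the prompt checks cover.** Post-Tx questioning at visits 1 and 2 follows two drops. Suppose a symptom occurs independently with probability q per drop (an assumption). The chance that it appears at one or both of two drops is 1 − (1 − q)²:

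- q = 0.1: 1 − 0.81 = 19%, against 1 − 0.9²⁹ = 95% over all 29 drops
- q = 0.5: 75%
- q = 0.9: 99%

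A third checked drop, as the SAP schedule would imply, raises the first figure to 1 − 0.9³ = 27%. So a symptom felt with most drops should surface in clinic, while an intermittent one often would not.

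**Anesthetic.** Protocol 7.7.2 and 7.7.3 list staining and tonometry before the clinic drop; Protocol 7.4.5.7 and 7.4.5.1 use topical anesthetic for both. In that order, the drops with the promptest questioning go into recently anesthetized eyes. The documents do not say how long the effect lasts.

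**Size of any under-count (illustration only).** Recorded incidence = true incidence × s, where s is the share of affected subjects captured. No document gives s. For s from 0.5 to 1.0 and 22 subjects:

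- true 20%: recorded 10–20% (2.2–4.4 subjects)
- true 86%: recorded 43–86% (9.5–18.9 subjects)

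If 0.5–0.8 were instead the capture probability at each of three independent visits, then s = 1 − 0.5³ to 1 − 0.2³ = 88–99%, and a true 86% would be recorded as 75–85%. The answer is driven by the assumption.

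**The case against.** The strongest reply is that capture is better than it first looks. Incidence is per subject, so one positive answer at any visit is enough. Questioning is targeted, and the symptoms are listed in the same section of the protocol. AEs are asked about shortly after two drops, many home drops are recalled the next day, and spontaneous reports and unscheduled visits are available. Onset and resolution dates are recorded (Protocol 8.5.1), so persistence can be described. All of this stands, and it narrows the concern to mild, intermittent or first-dose symptoms.

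Three further cautions also stand. The diary form is not reproduced in the documents, so a symptom field cannot be ruled out; only its described use is known. The 86% comes from a solution with 0.1% naphazoline, 0.1/0.03 = 3.3 times the strength here, and its method of collection is not given. Procedure order may be arranged by the site (Protocol 7.5, 7.7), so the anesthetic effect is a possibility and not a certainty.

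A reader might infer more than this: that symptom AEs are under-counted by a known amount, that home symptoms are all recalled two to five days late, or that missed symptoms could tip the trial's conclusion. The documents support none of these. They give no capture rate, the delay runs from one day upward, and no symptom enters H0 or H1.

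What the reply does not remove is that no described record covers symptoms at the time of the home drops. The targeted questioning also has no stated checklist or recall window.

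**Conclusion.** The concern holds as a risk of under-reporting, limited to a secondary outcome. About 90–93% of applications are at home, the described diary counts applications only, and symptoms from those drops depend on questioning 1 to 5 days later or on spontaneous report. The two drops followed by prompt questioning may be affected by prior anesthetic. Any bias would run towards finding the product tolerable. Its size cannot be computed: the ranges above rest on assumed capture rates and include no loss at all. The primary hypothesis decision is unaffected. Frequency per drop could not be described in any case, although Protocol 3.1.2 does not ask for it. The change is worth making because it is cheap and bears directly on the reason given for the study, but the trial does not fail without it.

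**What to change.** In Protocol 7.5.10, with matching entries in 1.3 and Table v, add to the existing diary a tick-box entry per application or per day: none, burning or stinging, itching, blurred vision, redness, other, each graded mild, moderate or severe. Review it at visits 1 and 2 alongside the adherence check. Record positives as AEs, grouping recurrent identical instillation symptoms as one AE per subject. If the diary form already has such a field, state this in 7.5.10.

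In SAP 6.2.2, report the percentage of subjects with each symptom and, descriptively, the percentage of applications or days.

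No extra visit or procedure is needed. The costs are a higher recorded rate of mild transient symptoms, a few seconds per entry for the subject, and more review: at most 29 × 22 = 638 entries per application, or 8 × 22 = 176 per day. Each AE needs the fields in Protocol 8.5.1, which is why the grouping rule matters.
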